#### 4.8.1 ADAS-Cog

The ADAS-Cog is a rater-administered scale with eight performance subtests: Word Recall; Commands; Constructional Praxis; Naming; Ideational Praxis; Orientation; Word Recognition; Remembering Word Recognition Test Instructions. Three examiner ratings, Spoken Language, Language Comprehension, and Word Finding Difficulty, also are obtained. The test is scored in terms of errors, with higher scores reflecting poorer performance and greater impairment. Scores can range from 0 (best) to 70 (worst).

Please refer to Appendix 2 regarding prorating subtest scores when there are partially missing data.

#### 4.8.2 CDR Sum of Boxes

The CDR sum of boxes is a numeric scale used to quantify the severity of symptoms of dementia and it assesses a participant's cognitive and functional performance in six areas: memory, orientation, judgment & problem solving, community affairs, home & hobbies, and personal care. Scores in each of these are combined to obtain a composite score ranging from 0 (best) to 18 (worst). If any item is missing, the assessment is considered missing.

The CDR sum of boxes will be assessed at visits conducted in clinic or via remote communication. Only in-clinic assessments will be considered in the primary analysis; sensitivity analysis will include similar analysis including remote assessments.

#### 4.8.3 Analysis of the Co-Primary Outcome Measures

The primary analyses use the within-participant change in ADAS-Cog 11 and in CDR-SOB as the outcome in two separate similar mixed effects repeated measures models, including all available in-clinic outcomes during the double blind phase in the mITT population. Fixed effects in the models are APOE status (e4 carrier vs e4 noncarrier), MMSE (mild vs. moderate) status, site, baseline ADAS-Cog or CDR-SOB score, respectively, treatment group (active vs placebo), visit, visit x baseline score interaction, and visit x treatment group interaction. Visit is treated as a categorical variable. Sites with only one subject will be pooled together. Descriptive statistics showing the timing of the primary outcome assessment will be presented by treatment arm as well as break-outs by baseline characteristics (e.g. APOE status, Mild/Moderate status based on MMSE, age group, and sex).

A random effect will be included for participant. The within-participant covariance will be unstructured. If the model does not converge, MMSE status will be removed from the model. If the model still does not converge, the following structures for the within-subject covariance will be fit, sequentially, until the structure is found that results in convergence of the model: Huynh-Feldt, Toeplitz, Autoregressive (1), and Compound Symmetry. Error degrees of freedom will be calculated using the Kenward-Roger approximation if an unstructured covariance is used; otherwise, a sandwich estimator will be utilized to estimate the covariance structure and degrees of freedom will be calculated using the between-within method. For the ADAS-Cog 11and CDR-SOB, each primary endpoint will be tested using model-adjusted least squares means at the week 48 visit. Point estimates, standard errors, two-sided 95% confidence intervals, and p-values will be presented.

The two co-primary endpoints will be tested for significance using a hierarchical gatekeeper strategy which preserves a 5% family-wise type I error rate. If a significant improvement in ADAS-Cog 11 is found with BHV-4157 relative to placebo at 5% level, then a similar analysis to the above will be conducted comparing CDR-SOB between the BHV-4157 and placebo arms. If a significant difference is found in CDR-SOB at 5% level, then both ADAS-Cog 11 and CDR-SOB are declared significant at 5% joint significance level, using this hierarchical gatekeeper analysis strategy. If there is no significant difference in ADAS-Cog 11, then CDR-SOB cannot be found to have a significant difference. A significant difference on both co-primary endpoints (at the 5% level) must be found in order to meet the primary trial objective.

The following sensitivity analysis will be conducted to support the principal analysis, following the same methods as above.

1. Imputation for missing data. All available in-clinic data will be used. Multiple imputations will be used to fill in any missing assessments. The imputation model will be a MMRM model. The parameters of the imputation model will use data from the placebo arm only - a jump to reference approach as described by Ayela, Lipkovich, Molenberghs & Mallinckrodt and Carpenter, Roger & Kenward. This model will be used as the imputation model for both the treated arm and the placebo arm, The imputation model will follow that specified in the primary analysis plan, however incorporating the additional baseline covariates of age, ADAS-COG, CDR-SOB, ADCS-ADL, and the time-dependent COVID indicator specified below. Proper imputation from this model will be used, following Rubin and Tsiatis, in that the mth imputation is based on a new parameter  $\beta^{n}$ , drawn from a N( $\beta^{n}, \Sigma^{n}$ ) distribution, where  $\beta^{n}$  and  $\Sigma^{n}$  are the maximum likelihood estimates from the imputation model. The augmented data (observed data, completed by the imputed data) will then be analyzed as specified for the primary analysis. This analysis will provide a lower bound on the estimated efficacy, as described in section 4.2.1.1.

Inference will use the rules for multiple imputation as outlined in Rubin. 20 imputations will be used. This analyses will be implemented in PROC MI in SAS with the MONOTONE option using predictive mean matching (option REGPMM) with

K=20, or in a similar manner in R. The outcome variable will be imputed in a monotone sequential manner.

- 2. Investigation of the impact of COVID-19 will be conducted by the following separate analyses:
  - i) A fixed effect to indicate an assessment occurring after March 13 (during the COVID pandemic) will be added to the model ("COVID indicator"), as well as the interaction of the COVID indicator x time. If the model with the interaction term fails to converge, the interaction term will be omitted.
  - A fixed effect to indicate the timing of the Week 48 assessment will be included in the primary analysis model. The fixed effect will be subject-based and include 2 levels. The subjects either discontinuing early or completing their in-clinic assessment within the originally specified week 48 window (Days 323-372) will be in one level of the effect and subjects with their week 48 assessment in the expanded portion of the window (days 373-420) in the another level.
  - iii) Remote assessments will be included in the model, with the model as specified for the primary analysis.
  - iv) Remote assessments will be included in the model, with the model as specified for the sensitivity analysis which includes the COVID indicator.

Additional supplemental analyses will run the primary model for each of the co-primaries but only include in-clinic "on-treatment" assessments (i.e. done within 3 days of the final dose of double-blind medication – see Section 4.3). These analysis will assess a more hypothetical estimand which focus on the effect of the study medication as intended.

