MMRM, using multiple imputation from the control arm to complete assessments missing after discontinuation of study drug. This analysis assumes subjects who discontinue medication and are no longer assessed immediately become similar to subjects who never took any medication, and so provides a lower bound on efficacy, again under the MAR assumption that the time of stopping study medication depends only on past history and covariates

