#### 4.6 **Participant Disposition**

A summary of participant disposition will be tabulated for all participants by treatment group and overall, including:

- Number of participants enrolled and signed informed consent form
- Number of enrolled participants excluded from the study prior to randomization and reason for exclusion
- Number of participants randomized
- Number of participants treated in Randomization Phase
- Number of mITT participants in Randomization Phase
- Number of participants who completed the Randomization Phase
- Number of participants who prematurely withdrew from the Randomization Phase and reasons for withdrawal
- Number of subjects who entered the Extension Phase
- Number of subjects treated in Extension Phase
- Number of mITT subjects in Extension Phase
- Number of subjects who completed the Extension Phase
- Number of subjects who withdrew from the Extension Phase and reasons for withdrawal

A special form will collect information on whether a visit was impacted by the COVID-19 pandemic crisis and will be used for all visits on or after March 1, 2020. This form will collect the specific impact on the visit (i.e. missed visit, in-person visit not all assessments completed, in-person visit occurring earlier or delayed, remote visit video, and remote visit telephone) as well as how COVID-19 impacted on a given visit (i.e. subject diagnosed/quarantined, site closure/restricted access, subject unwilling/unable to come to site, other). If the subject is terminating the study prematurely the CRF will also collect whether the reason was related to COVID-19 (yes or no).

An additional summary will present the disposition of subjects whose discontinuation was indicated as being related to the COVID-19 pandemic crisis on the COVID-19 CRF.

For the randomized subjects active during COVID-19, the impact of the COVID-19 pandemic crisis on the study will be summarized by presenting (by treatment and overall):

- number and percentage of randomized subjects active in the double-blind phase during the pandemic crisis, as referenced by having at least one visit in the double-blind phase on after the March 13, 2020 National Emergency declaration

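### SAP 4.3.1.1 and 4.8.3 set different rules for which missing visits are imputed from placebo, and the steps in 4.8.3 do not secure the jump-to-reference method it names, so its lower-bound label is not supported

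*SAP*

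**What the plan says.** SAP 4.3.1.1, item 4, plans an MMRM "using multiple imputation from the control arm to complete assessments missing after discontinuation of study drug". Its rationale is that "subjects who discontinue medication and are no longer assessed immediately become similar to subjects who never took any medication". It calls the result a lower bound on efficacy, on the condition that the time of stopping drug is missing-at-random given history and covariates.

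SAP 4.8.3, sensitivity analysis 1, describes the same analysis in operational terms. On data: "All available in-clinic data will be used". On scope: "Multiple imputations will be used to fill in any missing assessments". On method: "The parameters of the imputation model will use data from the placebo arm only - a jump to reference approach", followed by "This model will be used as the imputation model for both the treated arm and the placebo arm". The imputation model follows the primary MMRM, which has an unstructured within-participant covariance. It adds baseline covariates and a time-dependent COVID indicator. The software step is PROC MI with MONOTONE and predictive mean matching (REGPMM, K=20), one visit after another, or something similar in R. The section then claims a lower bound and refers to section 4.2.1.1; the text it means is in 4.3.1.1.

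Two other sections bear on what counts as missing. SAP 4.8.2 states: "The CDR sum of boxes will be assessed at visits conducted in clinic or via remote communication", with only in-clinic scores in the primary analysis. The COVID-19 form in SAP 4.6 records reasons that include "site closure/restricted access, subject unwilling/unable to come to site".

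**The concern.** The SAP concedes in 4.3.1.1 that missing-at-random may fail when participants leave after stopping drug, and it offers this analysis as the check. Two things in the text undermine it.

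**Scope.** The sections give different rules for one analysis, and both cannot be followed. Under 4.8.3, someone still taking drug who misses an in-clinic score is imputed as if untreated. The rationale in 4.3.1.1 does not cover that person.

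**Method.** Jump-to-reference keeps a participant's deviation from the mean of their own arm and moves the mean to placebo once data are missing. No step in 4.8.3 does this. If a placebo-fitted model predicts each visit from the participant's own earlier scores as they stand, an active participant who had done better than placebo is predicted to go on doing better. That is copy-reference. It carries part of the on-drug benefit forward, contrary to the immediate-loss premise behind the bound.

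At stake are reproducibility and the meaning of the reported figure: two programmers could follow the text, get different values, and both report a lower bound.

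**Working it through.** **Planning inputs (SAP 4.2).** ADAS-Cog 11 effect 2.64, SD 6; CDR-SOB effect 0.95, SD 2.3; at most 26% dropout, leaving 124 per arm. The imputation section states no result to reproduce, but the planning figures do reproduce. A two-sided 5% t-test with 124 per arm gives power of 93.2% (SAP 92%) and 90.0% (SAP 90%). Joint power at correlation 0.45 is 85.7%, and 85.7% x 0.937 = 80.3% (SAP 80%).

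**Assumptions not in the documents.** SD also 6 at weeks 12 and 36; dropout spread evenly after weeks 12, 24 and 36; between-visit correlation 0.3 to 0.8, equal or AR(1); dropouts had the same benefit as completers while observed; all dropouts off drug. Two benefit profiles: linear growth to week 48, or full benefit by week 12.

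**Step 1, jump-to-reference.** Dropouts contribute no mean benefit: 0.74 x 2.64 = 1.954.

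**Step 2, copy-reference, closed form.** Estimate = 1.954 + 0.26 x (average benefit carried forward). With equal correlation r and k observed visits, each earlier visit has weight r/(1 + (k-1)r). Example with r = 0.5:

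- Linear (benefit 0.66, 1.32, 1.98 at weeks 12, 24, 36): carried forward 0.5 x 0.66 = 0.33; 0.333 x 1.98 = 0.66; 0.25 x 3.96 = 0.99. Average 0.66, so 1.954 + 0.26 x 0.66 = 2.13.
- Early (2.64 throughout): 1.32, 1.76, 1.98. Average 1.69, so 1.954 + 0.26 x 1.69 = 2.39.

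Over the whole correlation range: 2.02-2.19 (linear) and 2.05-2.55 (early).

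**Step 3, the same reading with the SAP's predictive mean matching.** Simulation of sequential REGPMM, K=20, fitted on placebo only, parameters redrawn for each imputation, 168 per arm, 2,500 trials, Monte Carlo SE 0.005-0.008:

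| Correlation | Linear, r = 0.3 / 0.5 / 0.8 | Early, r = 0.3 / 0.5 / 0.8 |
|---|---|---|
| Equal | 2.04 / 2.08 / 2.13 | 2.18 / 2.30 / 2.43 |
| AR(1) | 2.00 / 2.05 / 2.14 | 2.02 / 2.09 / 2.28 |

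The gap over 1.954 is 0.04-0.19 (linear) or 0.07-0.47 (early). Against the planning SE, 6 x sqrt(2/124) = 0.762, that is 6-25% or 9-62%. For CDR-SOB, jump-to-reference gives 0.74 x 0.95 = 0.70, against 0.72-0.77 (linear) or 0.73-0.87 (early).

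**Step 4, scope alone.** If a share q of the active arm lacks a week-48 in-clinic score while still on drug, and is imputed at the placebo mean rather than within arm, the ADAS-Cog estimate falls by q x 2.64. For illustration only, since the documents give no q: 2% gives 0.05, 5% gives 0.13, 10% gives 0.26. Missing intermediate visits matter little. When weeks 24 and 36 were shifted to the placebo mean for 30% of the active arm with week 48 observed, the week-48 estimate moved by 0.001 on average over 60 simulated trials (largest 0.03).

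**The case against.** **The scope conflict will rarely bite.** Protocol 8.1 allows remote safety visits only at visits other than week 48. Protocol 8.1.9 lets the week-48 visit be delayed, up to 60 weeks of treatment. SAP 4.3.8, Table 1, accepts scores from Day 295 to Day 420 as week 48. Remote scores have their own analyses in 4.8.3, items 2(iii) and 2(iv). This stands: on-drug missing week-48 scores are probably uncommon.

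**Scope does not inflate efficacy.** A reader might infer that the wider scope in 4.8.3 breaks the lower bound. It does not: if the drug works, imputing more active visits from placebo lowers the estimate. A reader might also suppose that a sizeable share of the missing are still on drug and so derive a wide range of results. The documents give no such share, and the 26% in SAP 4.2 is a dropout rate.

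**Jump-to-reference is named and cited, and should govern brief software notes.** This stands in part. The predictors that 4.8.3 adds are baseline covariates and the COVID indicator; earlier visits are not listed. If only baseline predictors enter, or if scores are centred by arm, the gap in step 3 is zero. Copy-reference is therefore an inference. But the model has an unstructured within-participant covariance, is fitted to placebo, is applied to both arms and is run visit by visit with no centring step. The text does not secure the named method, nor does it say how non-monotone gaps are filled before a MONOTONE step.

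**The larger gaps need favourable assumptions.** Also true: 0.47 requires equal correlation of 0.8 and full benefit by week 12. If dropouts had only half the benefit, the copy-reference estimates shrink to about 1.98-2.05 (linear) and 1.98-2.20 (early).

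**Conclusion.** The point holds in two parts of different strength.

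The scope conflict is certain from the text and needs no inference. Its likely effect is small and downward, and it is confined mainly to missing week-48 in-clinic scores in participants still on drug.

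The method gap rests on the most natural reading of the steps, not the only one. Under that reading the analysis gives 2.00-2.14 or 2.02-2.43 where jump-to-reference gives 1.95, given the assumed correlations, dropout timing and benefit profiles. The gap vanishes if there is no benefit before dropout or no correlation between visits. Because the text permits an estimate above the jump-to-reference value, the lower-bound label is not supported. Even true jump-to-reference is a bound only if active-arm participants with missing data do no worse than comparable placebo participants.

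A reader might go further and infer that the analysis is anti-conservative or that the trial's conclusion is at risk. Neither follows. In every scenario computed the estimate stays below the missing-at-random value of 2.64, and the primary MMRM, alpha and the success rule are unaffected. What is lost is the claimed bound and a reproducible result.

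**What to change.** Amend the SAP before unblinding:

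1. Use the 4.3.1.1 scope in both sections, in the same words: placebo-based imputation only for visits missing after drug discontinuation. Impute intermittent and on-drug gaps, including visits with only a remote score, under missing-at-random within arm.
2. Write steps in 4.8.3 that implement jump-to-reference: active-arm mean at observed visits, placebo mean at visits missing after discontinuation. Name the predictors, including earlier visits.
3. Replace the lower-bound claim in both sections with the term reference-based sensitivity analysis.
4. Correct the cross-reference from 4.2.1.1 to 4.3.1.1.

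The cost is SAP wording and modest programming. The narrower scope can make the estimate slightly less conservative if some participants with missing scores are still on drug. The primary analysis and sample size do not change.

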## **4 STATISTICAL METHODS**

#### 4.1 Sample Size Justification and Power

#### 4.2 Overall Study Power

Using approximately 336 randomized participants (with a 1:1 assignment approximately 168 per arm), this study has at least 80% power to reject the null hypothesis of no efficacy in favor of the alternative that BHV4157 is efficacious, given the assumption of a difference in the mean change from baseline to 12 months between the BHV-4157 arm and placebo arm of 2.64 points on the ADAS-Cog 11 and 0.95 points in CDR-SOB, and under a range of interim effect sizes which give 93.7% probability of proceeding at the interim analysis.

This calculation assumes no more than a 26% dropout rate, which would leave  $336 \times 0.74 = 248$  subjects available at the final analysis, or 124 per arm. The calculation also assumes a standard deviation of 6 points on the change in ADAS-Cog 11 in each arm at both 6 months and 12 months, and a standard deviation of 2.3 points on the change in in CDR-SOB at 12 months; in addition a correlation of 45% between 12-month-change on the co-primary ADAS-Cog11 and CDR-SOB endpoints is assumed. These assumptions are supported by published retrospective data from historical ADCS studies. The computations use a 2-sided 2-sample t-test at 5% alpha to approximate power.

Briefly, the statistical reasoning is as follows:

- 1. P(pass overall) = P(pass final | pass interim) P(pass interim) ≥ P(pass final) P(pass interim)
- 2. P(pass final) = P(pass final ADAS) P(pass final CDR | pass final ADAS)
- 3. Numerical integration shows that P(pass final CDR | pass ADAS) is about 3% greater than P(pass final CDR), given the assumed 45% correlation between these endpoints.

Hence, if P(pass interim) = 0.937, P(pass final ADAS) = 0.92, and P(pass final CDR) = 0.90, then P(pass overall)  $\ge 0.92 \text{ x} (1.03 \text{ x} 0.90) \text{ x} 0.937 = 0.80.$ 

With 124 subjects per arm, the unconditional power for the ADAS-COG endpoint is 92%, if the mean difference in change is 2.64 points with standard deviation of 6 points within each arm. At this sample size, the unconditional power for the CDR-SOB endpoint is 90%, if the mean difference is 0.95 points with standard deviation of 2.3 points within each arm. Hence, if the interim analysis has power 0.937 or greater to pass, the overall power is 80% or more following the statistical reasoning given above.

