#### 4.3.5 Subpopulations

The subgroups of interest for this study are:

- Sex
- APOE (e4 vs no or missing)
- Mild vs moderate (mild AD:MMSE 20 to 24; moderate AD: MMSE 14 to 19)
- Participation during Covid-19 (opportunity to complete randomization phase before March 13, 2020 vs on or after March 13, 2020)

Except where indicated otherwise, descriptive summaries will be provided for the co-primary endpoints for each subgroup.

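### The COVID-19 sensitivity models contain no treatment-by-COVID term, so agreement between model 2(i) and the primary analysis is not evidence that the treatment effect held up during the pandemic

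*SAP*

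**What the plan says.** The primary MMRM in SAP section 4.8.3 carries treatment through a main effect and a visit-by-treatment interaction, and each co-primary is tested on the adjusted means at Week 48. Item 2 of the sensitivity analyses then lists four COVID-19 models:

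- 2(i): "A fixed effect to indicate an assessment occurring after March 13 (during the COVID pandemic) will be added to the model", "as well as the interaction of the COVID indicator x time". The interaction is dropped if the model fails to converge.
- 2(ii): a participant-level main effect separating Week 48 assessments in the expanded part of the window (Days 373-420) from everyone else.
- 2(iii): the primary model with remote assessments added.
- 2(iv): the 2(i) model with remote assessments added.

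The SAP Revision History gives the purpose of the added analyses as assessing the pandemic's impact on the primary and secondary endpoints and key safety domains.

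SAP section 4.3.5 also defines a subgroup by whether the participant had the opportunity to complete the randomization phase before March 13, 2020. For such subgroups, "Except where indicated otherwise, descriptive summaries will be provided for the co-primary endpoints for each subgroup". A model-based subgroup analysis (an MMRM in each subgroup) is planned only for mild versus moderate MMSE status.

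**The concern.** All four models impose a single Week 48 treatment difference across both periods. The COVID terms in 2(i) can absorb a shift in scores that is common to both arms. They cannot show whether the drug-placebo difference itself was smaller, or larger, once follow-up was disrupted. The protocol's own provisions make such a change conceivable: a Week 48 visit delayed to as much as 60 weeks of treatment, remote safety visits and couriered study drug.

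At stake is how a null finding is read. If 2(i) matches the primary analysis, a clinical study report could cite that as robustness to the pandemic, when the same match would be expected had the effect disappeared for every pandemic-period visit.

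**Working it through.** **Inputs from SAP section 4.2.** Differences of "2.64 points on the ADAS-Cog 11 and 0.95 points in CDR-SOB"; a "standard deviation of 6 points on the change in ADAS-Cog 11 in each arm at both 6 months and 12 months"; SD 2.3 for CDR-SOB change. "This calculation assumes no more than a 26% dropout rate", which leaves 248 of 336, or 124 per arm. "The computations use a 2-sided 2-sample t-test at 5% alpha to approximate power".

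**The plan's own figures reproduce.** At 124 per arm, t-test power is 0.932 for ADAS-Cog (stated 0.92) and 0.900 for CDR-SOB (stated 0.90). The overall product is 0.92 x 1.03 x 0.90 x 0.937 = 0.799 (stated 0.80). The documents give no figure for the COVID-19 analyses.

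**Why 2(i) tracks the primary.** Adding a covariate moves the treatment contrast by roughly (covariate coefficient) x (difference between arms in the covariate's mean). Under 1:1 randomisation that difference averages zero. With half of Week 48 visits in the pandemic and 124 per arm, its SD is sqrt(0.25 x 2/124) = 0.064. If the effect is 2.64 before and 0 during, with no common shift, the pooled COVID coefficient is about 2.64/2 = 1.32, so the gap has SD of about 1.32 x 0.064 = 0.08 points.

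**Simulation.** 300 trials per setting; 168 per arm; visits at Weeks 12, 24, 36 and 48; unstructured covariance; 26% monotone dropout; placebo decline of 3.9 points. Assumptions that are not in the documents: uniform staggered enrolment, SD 4.5 at Week 12, autoregressive correlation 0.6, a common COVID shift of 0, 1.5 or 3 points, and the pandemic share f of Week 48 visits. Site, APOE and MMSE terms were omitted. Mean Week 48 ADAS-Cog benefit:

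| f | Effect before / during | Common shift | Primary | 2(i) | Expected: average over periods |
|---|---|---|---|---|---|
| 25% | 2.64 / 0 | 0 | 2.00 | 2.00 | 0.75 x 2.64 = 1.98 |
| 50% | 2.64 / 0 | 0 | 1.35 | 1.34 | 0.50 x 2.64 = 1.32 |
| 75% | 2.64 / 0 | 0 | 0.72 | 0.72 | 0.25 x 2.64 = 0.66 |
| 50% | 2.64 / 2.64 | 1.5 | 2.63 | 2.63 | 2.64 |

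With common shifts of 1.5 or 3 points the two means still agreed within about 0.02. Within a single trial the gap had SD 0.08 to 0.28, against a standard error of 0.75 to 0.79. Both estimates are diluted by (1 - f), and comparing them cannot reveal it.

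**What a treatment-by-COVID-by-visit term gives.** In the same simulation it recovered a difference of about 2.6 before the pandemic and about 0 during it. The interaction's standard error was about 1.3 at f = 50% and about 1.45 to 1.5 at 25% or 75%, with power 0.42 to 0.55. Part of that precision comes from the assumed correlation between visits.

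A four-cell calculation on 248 completers takes no credit for repeated measures: SE = sqrt[SD^2 x (2/124) / (f(1 - f))].

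| Endpoint | f | SE | 95% half-width | Power for complete loss |
|---|---|---|---|---|
| ADAS-Cog (2.64, SD 6) | 50% | 1.52 | 2.99 | 0.41 |
| ADAS-Cog | 30% | 1.66 | 3.26 | 0.355 |
| CDR-SOB (0.95, SD 2.3) | 50% | 0.58 | 1.15 | 0.37 |
| CDR-SOB | 30% | 0.64 | 1.25 | 0.32 |

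If the ADAS-Cog effect were only halved, power would be 0.14 at f = 50% and 0.12 at 30%.

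**The case against.** A reader might infer that a pandemic-related loss of effect would go unseen. The documents do not support that. SAP section 4.8.3 tabulates both co-primaries and their change from baseline, by visit, for the COVID-participation subgroup. SAP section 4.3.1.2 makes tabulations by randomized group, with n, mean and SD. A reader could take crude differences from that table and build unadjusted intervals. What is absent is an adjusted difference, a between-period contrast and a stated interval.

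A reader might also infer that these models can only agree with the primary analysis. For 2(i), agreement holds in expectation and to within a fraction of a standard error, not exactly; differential dropout or visit delay could unbalance the indicator. For 2(iv) the inference fails, because added remote data can move the estimate. Its like-for-like comparator is 2(iii).

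The defence of 2(i) itself is fair: it asks whether the estimate survives adjustment for a shift common to both arms, and it answers that. The primary estimand (SAP section 4.3.1.1) applies a treatment policy strategy to intercurrent events, so an effect averaged over pandemic visits is the declared target and not a hidden bias. Nothing in the SAP says that 2(i) demonstrates a constant effect.

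Finally, the added contrast would be weak. Its ADAS-Cog half-width exceeds the whole assumed effect, and visits after March 13 belong disproportionately to later enrollees, so a difference could not be attributed to the pandemic alone. These points limit the remedy to estimation; they do not supply the missing interval.

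**Conclusion.** The point holds as a gap in what the COVID-19 models can show. None of 2(i) to 2(iv) allows the treatment effect to differ by period, and agreement between 2(i) and the primary analysis is expected whether the effect is constant or abolished, so it should not be reported as evidence that the effect was unaffected. The primary test, its alpha and its stated power are untouched.

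The conclusion on 2(i) held at 25%, 50% and 75% of Week 48 visits in the pandemic, a share the documents do not give. It rests on randomisation balancing calendar time between arms, which the stratified permuted blocks support. The simulation covered ADAS-Cog only; the balance argument applies equally to CDR-SOB. An added contrast would be informative mainly through its interval: ADAS-Cog half-width about 3.0 to 3.3 points and power about 0.36 to 0.41 for complete loss, at an assumed share of 30% to 50%. This is a worthwhile minor improvement, not a defect in the primary analysis.

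**What to change.** As an exploratory extension of 2(i) and 2(iv), for both co-primaries, add treatment x COVID indicator at Week 48 (treatment x COVID x visit, for visits where every arm-by-period cell is occupied). Alternatively, run the primary MMRM within each level of the COVID-participation subgroup, as is already planned for MMSE status.

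Report the Week 48 treatment difference before and during the pandemic, and their contrast, each with a 95% confidence interval, labelled as estimation and not as a pass/fail test. State in the SAP that 2(i) as it stands adjusts for a shift common to both arms, and that 2(iv) is to be compared with 2(iii).

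The cost is SAP wording and one extra model per endpoint on data already collected, with no change to the primary analysis or alpha. The SAP should state two downsides: the contrast is imprecise, and period is confounded with enrolment order.
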